8.7.1.1 Camera Quality Control

Quality control of the PET/CT scanner will be maintained throughout the study according to departmental SOPs.

8.7.1.2 Image Acquisition

PET scan and Quantitation: Following administration of Ga-68 tracer, each subject will have a PET/CT scans at 60-90 min on a Siemens mCT PET/CT scanner by using 10-12 bed positions and 3 min/bed. The CT parameters used for attenuation correction CT (CAREDose-4D) include a fixed 100 mA tube current and a peak voltage of 120 kVp with a 5-mm reconstruction interval. The PET scans will be reconstructed by using a Siemens time of flight reconstruction method, TrueX-TOF UltraHD-PET with a Gaussian filter, scatter correction, and 5/21 iterations/subsets.

For the study, using the decay-corrected coronal anterior maximum- intensity projections of PET scans, regions of interest (ROI) will be drawn manually around the major organs (liver, kidney, spleen, lungs, heart) and any other tissues (tumor, muscle) showing visually appreciable Ga-68 uptake. Time-activity curves will be constructed by using values of whole-organ activity at the time of imaging.

Recently, several 18F labeled peptides have been evaluated for imaging studies and methods for quantifying biodistribution and tumor localization have been described.

We plan to follow similar methods in our protocol. The percent injected dose in each ROI and the clearance kinetics from each organ will be used to estimate the radiation dosimetry based on OLINDA/EXM for the adult male phantom.

In order to generate quantitative data of tumor localization for each Ga-68 tracer, SUVmean and SUVmax will be generated as previously described. When there is no resolution loss or uncertainty in the ROI boundary definition (such as in the liver), SUVmean will produce a reliable estimate. However, SUVmax may be a more reliable parameter since the maximum value within an ROI is typically invariant with respect to small spatial shifts of the ROI.

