1 PROTOCOL SUMMARY

1.1 SYNOPSIS

Title:	Comparison of 68Ga-PSMA Positron Emission Tomography (PET)/CT to Conventional Imaging in Men with High Risk Prostate Cancer
Study Description:	This is a prospective, single-center, open-label pilot study of 68GA-PSMA-11 given at a single time prior to PET/CT imaging in men with localized high risk prostate cancer or biochemical recurrence. Eligible participants will undergo baseline assessments using conventional 99-Tc Bone Scan and CT of the Abdomen and Pelvis or multi-parametric MRI imaging of the prostate

Objectives:

Primary Objective

1. To evaluate the tissue distribution of 68GA-PSMA-11 PET/CT imaging in normal tissues and biopsy proven tumor and non-tumorous regions of the prostate, and also pelvic lymph nodes in high risk patients undergoing standard of care prostatectomy and bilateral lymph node dissection.
2. To determine the proportion of patients in which 68GA-PSMA-11 PET/CT altered the planned clinical management.

Secondary Objective:

1. To correlate the intensity of 68GA-PSMA-11 PET/CT uptake with respect to pathological findings.
2. To compare suspicious lesions visualized on 68GA-PSMA-11 PET /CT with standard of care diagnostic imaging modalities, additional biopsy results, or clinical follow-up performed at the discretion of the referring physician.

Endpoints:

Primary Endpoints:

1. Proportion of patients with cTxNoMo (clinically localized disease) found on final histological examination to have lymph node involvement as determined by 68GA-PSMA-11 PET/CT.
2. Proportion of patients in which 68GA-PSMA-11 PET/CT altered the planned clinical management.

Secondary Endpoints:

1. 68GA-PSMA-11 PET/CT intensity is variable, and we will evaluate what intensity endpoint is predictable of tissue involvement.
2. To compare and contrast findings in 68GA-PSMA-11 PET/CT with standard diagnostic modalities of bone scan, CTs and MRIs.

Study Population: Male patients, aged 21 or older, diagnosed with histopathological proven prostate adenocarcinoma, with no evidence of other malignancy, and Eastern Cooperative Oncology Group (ECOG) performance of 0-1.

Phase: Pilot, phase I/2

Description of Sites/Facilities
This is a single site trial that will be conducted at the Houston Methodist Hospital.

Enrolling Participants:

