4 STUDY DESIGN

4.1 OVERALL DESIGN

This is a prospective, open label, single-center, single-arm, pilot diagnostic accuracy study to evaluate the tissue distribution of 68Ga-PSMA Positron Emission Tomography (PET)/CT in 80 patients with high risk localized prostate cancer or biochemical recurrence.

At screening: participants will sign an approved informed consent, medical history and vital signs will be completed. Labs will be drawn for PSA. Eligibility criteria will be verified and completed.

Day of the injection:

Subjects will receive a single IV dose of 3-7 mCi of 68Ga-PSMA (study drug) followed by PET/CT imaging 60-90 minutes after injection. Scan time will be determined based on the capacity of the PET scanner. Scanning will start from the mid-thighs (to minimize radiotracer artifact from accumulation in the bladder) to the base of the skull. There may be exceptions based on clinical relevance that the scan coverage may be extended.

All patients will be closely monitored with vital signs, to be assessed before and after injection of 68Ga-PSMA-11 (Blood Pressure, Heart Rate). Patients will be monitored with respect to vital signs and adverse events during, and 2-hours following radiotracer administration for adverse events.

Post injection:

Patients will receive a phone call 2 days following PET/CT to assess for adverse events that may have developed in a delayed fashion. If there are any concerning study-related adverse events, this will be escalated to clinical evaluation by the study primary investigators.

To minimize bias, all PET/CT images will be interpreted by a board certified radiologist with experience in reading such modalities. They will be blinded to the final outcome, such as the histopathology of any biopsies and the outcome of subsequent imaging.

68-Ga-PSMA PET/CT positivity or negativity will be interpreted, stratified by different anatomic regions as previously defined [1].

REGION DESCRIPTION

1	Prostate and Prostate Bed
2	Pelvis, excluding prostate bed, but including lymph nodes
3	Extra-pelvic soft tissue, including lymph node involvement and metastasis to other organs
4	Bone Metastasis

The presence of prostate cancer (positive or negative) will be reported within these regions.

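### Uptake regions are to be drawn on coronal maximum-intensity projections, which cannot yield whole-organ activity or percent injected dose and give an unreliable SUVmean and a conditional SUVmax

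*Combined protocol and SAP*

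**What the plan says.** Section 8.7.1.2 (Image Acquisition) names one image for region drawing: "using the decay-corrected coronal anterior maximum- intensity projections of PET scans, regions of interest (ROI) will be drawn manually around the major organs". The organs listed are liver, kidney, spleen, lungs and heart. The same step covers "any other tissues (tumor, muscle) showing visually appreciable Ga-68 uptake", which is how prostate lesions and nodes enter, since neither is named.

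The section then asks for three kinds of quantity:

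- Whole-organ activity: "Time-activity curves will be constructed by using values of whole-organ activity at the time of imaging".
- Percent injected dose, as input to OLINDA/EXM: "The percent injected dose in each ROI and the clearance kinetics from each organ will be used to estimate the radiation dosimetry".
- Standardized uptake values: "SUVmean and SUVmax will be generated as previously described". No description or citation is attached at that point.

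No section describes a volume of interest on axial or three-dimensional data, a segmentation threshold, or a CT-based organ boundary.

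Two objectives in the synopsis and section 3 depend on measured uptake. Primary objective 1 is "To evaluate the tissue distribution of 68GA-PSMA-11 PET/CT imaging in normal tissues and biopsy proven tumor and non-tumorous regions of the prostate", together with pelvic nodes. Secondary objective 1 is "To correlate the intensity of 68GA-PSMA-11 PET/CT uptake with respect to pathological findings".

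**The concern.** The image named for measurement does not contain what the measurements need. Activity and percent injected dose are sums over a volume, and a coronal MIP is a flat picture of maxima. An SUVmean taken from it is not a mean of the tissue, and an SUVmax taken from it may belong to something in front of or behind the tissue.

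At stake are the descriptive tissue-distribution results, any uptake level proposed as predictive of tissue involvement, and the dosimetry estimate. Primary objective 1 contrasts tumor with non-tumorous prostate, and section 8.9 makes tumor foci on H&E sections the reference. In a frontal projection, tumor lying in front of or behind benign prostate supplies the value for both. Section 4.2 intends the results as preliminary data for later studies, so a measurement error here would be carried forward.

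**Working it through.** The documents give no figure on this point, so there is none to reproduce. The check uses the definition of a MIP, then numerical phantoms. Every SUV, size, resolution and noise level in the phantoms is an assumption; section 8.7.1.2 mentions a Gaussian filter but not its width, and gives no noise level.

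**Definition.** With S(x,y,z) the uptake and y the front-to-back axis, MIP(x,z) = max over y of S(x,y,z).

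**1. Whole-organ activity and percent injected dose.** Activity = sum over organ voxels of (concentration × voxel volume); percent injected dose = 100 × activity / injected activity. Both need the depth of the organ along each ray.

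- Two blocks of equal uptake and equal frontal outline, 5 and 40 voxels deep, gave identical MIPs. Their activities differ by 40/5 = 8-fold.
- If the MIP pixels of a sphere are summed as a slab one voxel thick (60 mm radius, 4 mm voxels), the result is 221 of 4356 SUV·mL (5%) with no noise and 296 of 4359 (7%) at 20% noise.

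The first result needs no assumption about noise or size.

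**2. SUVmean.** For ray r with depth d_r inside the organ and mean m_r along it:

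- volume mean = Σ(d_r × m_r) / Σ d_r
- MIP-region mean = average over rays of the ray maximum

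Each ray maximum is at or above its own ray mean. In a roughly uniform organ the MIP mean is therefore biased upward.

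*Phantom A* (sphere of SUV 5 in background 0.5, light smoothing, independent voxel noise; volume mean 4.81):

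| Voxel noise | MIP mean | Ratio to 4.81 |
|---|---|---|
| 0% | 4.86 | 1.01 |
| 10% | 5.67 | 1.18 |
| 20% | 6.53 | 1.36 |

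*Phantom B* (SUV 5 in background 1, 4 mm voxels, 6 mm resolution, spatially correlated noise). Ratio of MIP mean to volume mean by sphere radius; where repeat runs differed, the range is shown:

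| Voxel noise | 1 cm | 2.5 cm | 5 cm |
|---|---|---|---|
| 0% | 1.06–1.08 | 1.03 | 1.02 |
| 5% | 1.08 | 1.08 | 1.09 |
| 10% | 1.09 | 1.13–1.14 | 1.16 |
| 20% | 1.15–1.18 | 1.23–1.24 | 1.31 |

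The bias shrinks with size when there is no noise, is about flat at 5%, and grows with size at 10% and 20%.

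In an uneven organ the direction can reverse, because the MIP weights rays equally and the volume mean weights them by depth. Take two rays of equal area, one 10 voxels deep at SUV 10 and one 1 voxel deep at SUV 4:

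- MIP mean = (10 + 4)/2 = 7.0
- volume mean = (10×10 + 1×4)/11 = 104/11 = 9.45
- ratio = 7.0/9.45 = 0.74, an understatement of 26%

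**3. SUVmax.** A small lesion was placed on the same rays as a larger structure:

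| Lesion SUV | Overlapping SUV | MIP maximum |
|---|---|---|
| 3 | 2 | 3 |
| 3 | 20 | 20 |
| 10 | 10 | 10 |
| 10 | 40 | 40 |
| 20 | 10 | 20 |

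The lesion's maximum survives when it is at least as hot as anything on its ray, and is lost otherwise. Section 4.1 recognizes a candidate for overlap in the pelvis, since the scan direction is chosen "to minimize radiotracer artifact from accumulation in the bladder". Section 2.2 lists kidney and small intestine among PSMA-expressing tissues.

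**4. Same phantoms, values from three-dimensional volumes.** In Phantom A the organ mean was 4.81 at every noise level. The lesion's own SUV was unchanged whatever the overlapping uptake.

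**The case against.** The strongest reply is that section 8.7.1.2 says regions are drawn using MIPs, not that values are read from MIP pixels. Whole-organ activity is a volumetric term, the section defers to published methods, and its remark that SUVmean is reliable in liver fits three-dimensional measurement. The authors may have meant the MIP for locating tissue only. That is possible, and it means one cannot say the values will in fact be taken from the MIP. But the text nowhere says otherwise, and percent injected dose is tied to each region so drawn. An uncited reference to earlier description does not displace an explicit instruction.

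Other points on this side stand:

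- A reader might infer that MIP means always overstate tissue uptake. They do not; the 7.0 against 9.45 example shows the opposite.
- A reader might infer that urinary activity will replace prostate and node values. That happens only where hotter activity shares the ray. The documents give no frequency of overlap, and scan direction (section 4.1) with hydration and voiding (section 5.3.1) should reduce bladder activity.
- A reader might infer that the primary endpoints are compromised. Both are patient proportions, one for nodal involvement and one for changed management. PET positivity is a regional read against blood pool or local background (sections 4.1 and 8.7.1) and is not tied to the MIP.

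**Conclusion.** The point holds as a wrong measurement rule in the current text. Followed literally, section 8.7.1.2 makes whole-organ activity and percent injected dose unrecoverable, replaces SUVmean with a different quantity, and makes SUVmax valid only when the target is the hottest tissue on its ray. The first of these follows from the definition of a MIP alone.

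The size of the SUVmean error is not known for this trial. The phantom ratios of 1.01 to 1.36 are illustrative, apply to uniform spheres, and depend mainly on the assumed noise. For uneven organs neither size nor direction can be stated in advance. The size and frequency of the SUVmax error depend on anatomy and urinary activity that the documents do not quantify.

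The reach is limited to the descriptive part of primary objective 1, the intensity-versus-pathology secondary endpoint, and the dosimetry, which is not itself a listed endpoint. The two primary endpoint proportions are not directly affected. The documents do not support a claim that the study's imaging data are unusable: the reconstructed PET volumes would allow correct measurement.

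**What to change.** Replace the region-drawing sentence in section 8.7.1.2 with:

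*Volumes of interest will be drawn on the reconstructed three-dimensional PET data, with CT for anatomical boundaries. SUVmean, SUVmax and percent injected activity will be taken from these volumes. Prostate, prostate-bed and pelvic-node volumes will exclude urinary activity. MIP images will be used for orientation only.*

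State the boundary rule, or cite the specific source, where the text now says only that SUVs follow an earlier description. If the MIP was always meant for localization only, the same wording corrects the text.

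The cost is somewhat more contouring time. The PET volumes and CT are already acquired, so no extra scan, patient or reader is needed. One limit remains: section 2.3.3 describes the CT as non-diagnostic and section 8.7.1.2 gives it a 5-mm reconstruction interval, so boundaries of small structures will carry some uncertainty.

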8.8 Prostatectomy

Subjects will undergo standard of care surgery as deemed appropriate by the patient's attending urologist.

8.9 Surgical Pathology

Following radical prostatectomy and/or pelvic lymph node dissection, surgical specimens will be brought on ice to the Department of Surgical Pathology for tissue processing. Prostatectomy and lymph node specimens will be processed by the Department of Pathology in the standard fashion with hematoxylin and eosin (H&E) staining for grading and staging. Additionally, immunohistochemistry will be performed to confirm, at a microscopic level, that radiolabeled 68Ga-PSMA-11 co-localizes with tumor foci seen on H&E sections. Tumor foci identified on H&E sections will serve as the gold standard for imaging comparison.

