Description of Study Intervention: This is a prospective, open label, single-center, single-arm, pilot diagnostic accuracy study to evaluate the tissue distribution of 68Ga-PSMA Positron Emission Tomography (PET)/CT in 80 patients with high risk localized prostate cancer or biochemical recurrence.

Subjects will receive a single IV dose of 3-7 mCi of 68Ga-PSMA (study drug) followed by PET/CT imaging 60-90 minutes after injection. All patients will be closely monitored with vital signs (blood pressure and heart rate), before and 2 hours following radiotracer administration.

Patients will receive a phone call 2 days following PET/CT to assess for adverse events.

To minimize bias, all PET/CT images will be interpreted by a board-certified radiologist. The radiologist evaluating the images will be blinded to the final outcome, such as the histopathology of any biopsies and the outcome of subsequent imaging.

Patients with study-defined high-risk features who are eligible and scheduled for radical prostatectomy or with biochemical recurrence will undergo 68Ga-PSMA-11 PET/CT injection. The results of the 68Ga-PSMA-11 PET/CT may alter patient

management in one of several ways, including the decision to not pursue surgical extirpation (e.g. in the event of extensive distant metastasis) in favor of systemic therapy. It is also possible that the extent of surgical resection may be altered, such as non-regional pelvic or retroperitoneal lymph node dissection. The alteration in planned surgical treatment from standard of care will be recorded as a secondary-end point.

Study Duration: 18 months.
Participant Duration: 6 months.

SCHEMA

Screening
Visit 1

Total:80 patients - Obtain informed consent. Screen potential participants by inclusion and exclusion criteria; obtain history, physical exam, height/weight, ECOG, safety labs

Visit 2

Administration of study intervention.
AE assessment (Phone follow-up)

Radical Prostatectomy

Systemic Therapy to be
determined attending
physician if metastatic disease
is identified

Follow up at 2 and 6 months

Visit 3 and 4

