6.3 MEASURES TO MINIMIZE BIAS: RANDOMIZATION AND BLINDING

To minimize bias, all PET/CT images will be interpreted by a board-certified radiologist. The radiologist evaluating the images will be blinded to the final outcome, such as the histopathology of any biopsies and the outcome of subsequent imaging.

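### H&E histology is the gold standard for PET, but nothing requires the nodal H&E call to be made without knowledge of the PET result

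*Combined protocol and SAP*

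**What the plan says.** Section 4.1 describes the study thus: "This is a prospective, open label, single-center, single-arm, pilot diagnostic accuracy study". Section 6.3 contains one safeguard: "The radiologist evaluating the images will be blinded to the final outcome, such as the histopathology of any biopsies", which it extends to later imaging. Sections 1.1 and 4.1 repeat it. No other blinding is described.

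Section 8.9 covers the other side of the comparison. On handling: "Prostatectomy and lymph node specimens will be processed by the Department of Pathology in the standard fashion", with H&E staining for grading and staging. On the added stain: "immunohistochemistry will be performed to confirm, at a microscopic level, that radiolabeled 68Ga-PSMA-11 co-localizes with tumor foci seen on H&E sections". On the reference: "Tumor foci identified on H&E sections will serve as the gold standard for imaging comparison". The section does not say whether the pathologist knows the PET result, how nodes are sampled, or how thoroughly they are sectioned.

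On order, Sections 1.2 and 4.1 place PET before surgery. Section 1.1 lets the PET result change the operation: "It is also possible that the extent of surgical resection may be altered, such as non-regional pelvic or retroperitoneal lymph node dissection". The treating team therefore knows the result before there is a specimen.

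**The concern.** In an accuracy study each test should be read without the other. Here only the index test is protected. The reference test comes second, in an open-label, single-center setting, after a PET result on which the surgical team may already have acted.

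Small nodal deposits are found in proportion to how hard one looks. If effort depends on PET, the reference standard is no longer independent of the test it judges. Three results are exposed (Section 3):

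- Primary endpoint 1, which combines PET and final histology at the nodes.
- Secondary endpoint 1, which looks for the uptake intensity that predicts tissue involvement.
- Secondary endpoint 2, which compares PET with bone scan, CT and MRI, and whose justification rests on histology.

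Section 4.2 intends the results as preliminary data for further studies, so a distorted estimate would be carried forward.

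**Working it through.** **No plan figure to reproduce.** Section 9.1 says the sample size was not statistically determined. The protocol gives no assumed sensitivity for PSMA PET, no nodal prevalence and no pathology detection rate. All inputs below are assumptions.

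**Apparent sensitivity.** Let Se be true PET sensitivity for nodal disease. Let d1 and d0 be the probabilities that pathology finds a true nodal metastasis in PET-positive and PET-negative men. Then

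apparent sensitivity = Se·d1 / (Se·d1 + (1 − Se)·d0).

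Example: Se = 0.60, d1 = 1.00, d0 = 0.80 gives 0.60 / (0.60 + 0.40 × 0.80) = 0.60 / 0.92 = 0.652. With d1 = d0 = 0.80 it is 0.48 / (0.48 + 0.32) = 0.600, so there is no bias.

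| d0 | d1 | Se 0.40 | Se 0.60 | Se 0.80 |
|---|---|---|---|---|
| 0.90 | 0.90 | 0.400 | 0.600 | 0.800 |
| 0.90 | 1.00 | 0.426 | 0.625 | 0.816 |
| 0.80 | 1.00 | 0.455 | 0.652 | 0.833 |
| 0.70 | 0.90 | 0.462 | 0.659 | 0.837 |
| 0.70 | 1.00 | 0.488 | 0.682 | 0.851 |

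Across this grid the excess runs from 0 to 8.8 points (0.488 − 0.400).

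**Joint yield (primary endpoint 1).** Expected PET-positive, histology-positive men = N × prevalence × Se × d1. Take N = 80 as an upper bound, since the 80 include men with biochemical recurrence. With Se = 0.60:

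- Prevalence 0.15: 80 × 0.15 × 0.60 × 0.80 = 5.76, rising to 7.20 at d1 = 1.00.
- Prevalence 0.30: 11.52, rising to 14.40.

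The relative rise is 1.00 / 0.80 = 1.25 whatever N, prevalence and Se are.

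**Comparison with conventional imaging (secondary endpoint 2).** Take 100 truly node-positive men and Se = 0.60. With detection 0.80 in both groups, pathology confirms 48 PET-positive and 32 PET-negative men, 80 in all. With d1 = 1.00 it confirms 60 + 32 = 92. All 12 extra men are PET-positive. If conventional imaging finds disease independently of PET, its apparent sensitivity is unchanged, while PET's goes from 48/80 = 0.600 to 60/92 = 0.652. The difference moves 5.2 points toward PET. If conventional imaging tends to flag the same men as PET, the shift is smaller.

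**Intensity cut-off (secondary endpoint 1).** The observed probability of tumor at a given uptake is the true probability times the detection probability at that uptake. If detection rises with uptake, the observed curve is too steep. The documents do not allow the shift in the cut-off to be sized.

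**The case against.** Much of the case on the other side stands, and it limits what can be claimed.

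- *A reader might infer that pathology is told the PET result.* The documents do not say so. They show that the treating team knows it; pathology's access is plausible but undocumented.
- *A reader might infer that a PET-guided search is planned.* It is not. Standard processing weighs against it, and no extra levels or re-look are described. But standard processing neither masks the pathologist nor fixes the sectioning.
- *A reader might take the immunohistochemistry as a hunt for missed deposits.* As written, it is applied to foci already seen on H&E, and H&E alone is the gold standard. The order is implied; what is missing is a recorded call before the correlation starts.
- *A reader might dismiss the reader blinding as empty because PET precedes surgery.* It also covers biopsies, which Section 1.2 places at screening, so it does real work.
- *A reader might call any rise in positive predictive value bias.* Tumor found on a re-look is real tumor. The distortion comes from unequal search, and is clearest in sensitivity and in comparisons between modalities. The joint yield then reflects search effort as well as the test.

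It can also be said that this is an exploratory, descriptive pilot in which sampling error dominates. A yield of 8/80, for instance, has an exact 95% interval of 4.4% to 18.8%, while the shift above at prevalence 0.15 is from 5.76/80 = 7.2% to 7.20/80 = 9.0%. That is fair on size. But the interval does not show the bias, and more patients would not remove it. Sensitivity is not a named endpoint; the two histology-based secondary endpoints are exposed all the same.

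**Conclusion.** The gap is real and narrow: the plan masks the index test and leaves the reference standard without protection against knowledge of PET. Whether bias arises depends on what pathology sees and does, which the documents do not state. Under the assumed values, apparent sensitivity would be too high by 0 to 8.8 points, with 0.60 read as 0.65 in the central example. A rise in PET-positive detection from 0.80 to 1.00 would lift the joint yield by a quarter. Equal detection removes this bias entirely, and no change to the sample size follows. The change is worth making because it is cheap and because a PET-naive first call cannot be reconstructed once PET-informed review has taken place.

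**What to change.** Add to Sections 6.3 and 8.9:

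1. The initial H&E call for each node packet is made without the PET findings, with the same sectioning whatever PET showed.
2. That call is recorded and dated before any PET-guided re-look or immunohistochemistry correlation.
3. The masked H&E call is the gold standard for the imaging comparisons.
4. Primary endpoint 1 is reported with both the masked call and final histology. The endpoint is defined on final histology, so the masked call should not silently replace it.
5. Foci found only after PET-informed review are listed separately.

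PET stays available to pathology once the call is recorded, so clinical reporting still has the full information.

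The cost is a few sentences, a date field, a small change to the sign-out workflow in what is otherwise standard-of-care pathology, and a short delay before PET-informed review. The change does not deal with PET altering which nodes are resected (Section 1.1). That is a separate dependence of histology on PET, which masking the pathologist cannot remove.
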